## 11. Risks and Benefits

### 11.1. Potential Risks

Risk with Sensors	Prevention and Mitigation
Risks with Sensors may include: 

• Skin irritation or reaction to adhesives

• Bruising

• Discomfort

• Redness

• Bleeding

• Excessive bleeding due to anticoagulants

• Pain

• Rash

• Infection

• Irritation from tapes used with glucose-sensing products

• Raised bump

• Appearance of a small "freckle-like" dot where needle was inserted

• Allergic reaction

• Syncopal episode secondary to needle insertion

• Soreness or tenderness

• Swelling at insertion site

• Sensor fracture, breakage or damage

• Minimal blood splatter associated with sensor needle removal

• Residual redness associated with adhesive and or tapes

• Scarring

• Scab

• Blister

• Itchiness

• Inflammation

• Anxiety

• Anxiety associated with insertion

	Prevention and mitigation include: 

• Follow the provided user guides for insertions and care of sensors.

• If a sensor site becomes infected or inflamed, the sensor should be removed and another placed in a new location

Risks with Transmitter	Prevention and Mitigation
Risks with Transmitter may include:	Prevention and mitigation include:

# CIP324 Clinical Investigation Plan

10838519DOC

Version H

Page 124 of 173

Medtronic

• Skin irritation or reaction to adhesives

• Bruising

• Discomfort

• Redness

• Pain

• Rash

• Infection

• Irritation from tapes used with glucose-sensing products

• Raised bump

• Allergic reaction

• Soreness or tenderness

• Residual redness associated with adhesive and/ or tapes

• Scarring

• Scab

• Blister

• Itchiness

• Inflammation

	

• Follow the provided user guides for transmitters.

• Training on proper use of the transmitters.

Risks with Serter Risks with Serters may include: 

• Improper insertion may lead to device performance issue or hyperglycemia

	Prevention and Mitigation Prevention and mitigation include: 

• Follow the provided user guides for insertions and care of Serters.

• Training on proper use of the Serter and skin preparation prior to insertion.

Risks with Finger Sticks Risks with frequent finger stick testing may include: 

• Potential risks associated with frequent meter testing of blood glucose and blood ketones include discomfort and ecchymosis at tips of fingers

• Potential risks associated with finger stick testing include discomfort and bruising

	Prevention and Mitigation Prevention and mitigation include: 

• Follow the provided user guides for use of meter with fingerstick testing.

• Training on proper use of the meter and fingerstick testing.

---

**Medtronic Confidential**

This document is electronically controlled

056-F275, vA Clinical Investigation Plan Template

# CIP324 Clinical Investigation Plan

10838519DOC

Version H

Page 125 of 173

Medtronic

Risks with IV Catheter Insertion	Prevention and Mitigation

Risks with IV catheter insertion may include:
 

• Pain

• Bruising

• Infection

• Irritation

• Syncopal episode secondary to catheter insertion

• Swelling.

• Discomfort

• Anxiety

	
Prevention and mitigation include:
 

• Qualified individual to perform IV catheter insertion

• Constant observation and monitoring of the subject during challenges

• Sterile technique will be used to insert the IV

 
Treatment of these risks include:
 

• Removal of IV catheter if subject experiences significant discomfort

• Removal of IV catheter if infection develops

• Antibiotics should be given, if needed

Risks for indwelling IV catheter	Prevention and Mitigation

Risks with indwelling IV catheters may include:
 

• Infection

• irritation

• swelling

• thrombosis

• phlebitis

• bruising

	
Prevention and mitigation include:
 

• Management of IV per investigational center protocol

• Use of universal precautions to avoid infection

• Qualified investigator presence during experiment

• Constant observation and monitoring of the subject during challenges

• Observation for redness at IV insertion site by qualified staff

 
Treatment of these risks include:
 

• Removal of IV catheter if infection develops and antibiotics should be given.

Risks with Blood Draw	Prevention and Mitigation

Risks with drawing blood may include:
 

• Discomfort and bruising

• Insertion of an IV catheter and drawing blood may also result in faintness, inflammation of the blood vessel, pain and bruising at the needle site

• There is also a slight possibility of infection.

	
Prevention and mitigation include:
 

• Qualified staff to perform blood draw

Risks with IV Saline Infusion	Prevention and Mitigation

Risks with saline infusion may include:
 

• Edema

• Congestive heart failure

• Third spacing

	
Prevention and mitigation include:
 

• Qualified investigator presence during experiment

• Constant observation and monitoring of the subject during challenges

 
Treatment of these risks include:

*Medtronic Confidential*

This document is electronically controlled

056-F275, vA Clinical Investigation Plan Template

# CIP324 Clinical Investigation Plan

10838519DOC

Version H

Page 126 of 173

Medtronic

	

Reduction of IV fluid if subject shows signs of CHF, lower extremity edema, crackles on lung auscultation or S3 heart sound

 
Subjects who still exhibit signs of fluid overload at time of discharge will be transported to the emergency room (ER) or follow guidelines of the local institution for the disposition of subject.

Risks with hyperglycemic challenges	Prevention and Mitigation 
Risks with hyperglycemia may include:
 

Diabetic ketoacidosis

Symptomatic ketosis

Cardiovascular event

Dehydration

Potassium and sodium imbalance

Shock

Altered mental status

Coma

Acidosis

 
Prevention and Mitigation include:
 

Follow frequent blood sampling per protocol (See Section 10.5.1)

Clear guidelines for management during hyperglycemic challenge

IV access to give immediate insulin

Qualified investigator presence during experiment

Stopping challenge procedures if ketones are elevated or subject is exhibiting signs and symptoms of DKA (Please refer to the ketone management guidelines in the protocol)

Limiting the time the subject is allowed to stay in the hyperglycemic ranges

The subject is under constant observation and monitoring at all times during the challenges

Preventing subjects who do not have a carb/insulin ratio and insulin sensitivity factor from participating in the challenge (observational only)

Investigational centers are to use glucose meter in the event a FST blood glucose value is not available at the required time interval.

Follow the Ketone management instructions per protocol

 
Treatment of these risks include:
 

IV fluid administration with 0.9 NS will at a rate of 100 cc per hour if ketonemia develops

Rescue therapy management treatment guidelines are provided in the protocol for hyperglycemic events

IV insulin administration will be per the institutions DKA protocol if DKA is suspected

Immediate withdrawal from study if subject is exhibiting signs and symptoms of DKA (Stop the challenge, stop the FST and DO NOT continue with any future scheduled frequent sampling days).

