## **Hypoglycemic and Hyperglycemic Challenges**

During the YSI™\* FST, subjects with a known insulin sensitivity ratio and insulin carbohydrate ratio will be randomly assigned to undergo hypoglycemic and hyperglycemic challenges (see Hypoglycemic and Hyperglycemic Challenge Guidelines).

Subjects will continue with their current diabetes regimen independent of the study devices. Subjects will be instructed by the investigational center that they are not to use the study devices (except for the study meter) for the management of their diabetes.

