## Hypoglycemic and Hyperglycemic Challenges

### **Subjects 2 - 13 years:**

During the day of YSI™\*/SMBG FST, subjects (2 - 13 years) will not participate in hypoglycemic and hyperglycemic challenges.

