### **10.5.4. Treatment Guidelines Based on Ketones (Investigator Discretion May Be Used for Medical Management)**

- a) Ketone level greater than or equal to ( $\geq$ ) 0.6 mmol/L and less than ( $<$ ) 3.0 mmol/L with no symptoms of ketoacidosis (nausea, vomiting, or abdominal pain) and for glucose less than or equal to ( $\leq$ ) 500 mg/dL the following should occur:

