## For Ketones greater than or equal to ( $\geq$ ) 0.6 mmol/L and less than or equal to ( $\leq$ 1.5) mmol/L

- In-clinic procedures may continue
- Administer oral hydration with sugar free, caffeine free liquids (if subject is able to drink) or IV fluid hydration (if needed):
  - 22 years and older: 100 cc/hour of 0.9 normal saline (NS) for 2 hours
  - 2-21 years rate for IV fluid hydration is 10 cc/kg given over 2 hours.
- If no nausea, vomiting, or abdominal pain, subjects may continue with hydration for a maximum of 2 hours with glucose greater than ( $>$ ) 250 mg/dL with ketones greater than or equal to ( $\geq$ ) 0.6 mmol/L and less than or equal to ( $\leq$ ) 1.5 mmol/L before insulin is administered
- The maximum amount of saline to be infused per kg during the YSI™\* FST is:
  - 60 ml/kg, however it is preferred to have no more than 50 ml/kg for (7 – 80 years).
  - 20 ml/kg for (2 – 6 years).
- For subjects treated with CSII, the catheter should be changed if glucose is greater than or equal to ( $\geq$ ) 250 mg/dL for 2 hours and insulin should be administered with a syringe
- If subjects develop nausea, vomiting, or abdominal pain, the study should be stopped.
- If subject shows signs of fluid overload (i.e., congestive heart failure (CHF), lower extremity edema, crackles on lung auscultation of S3 heart sound) then rate of IV hydration will be decreased to half the current rate

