- If subject shows signs of fluid overload (i.e., CHF, lower extremity edema, crackles on lung auscultation of S3 heart sound) then rate of IV hydration will be decreased to 50 cc/hour

c) Subject is exhibiting signs and symptoms of DKA. The following guidelines to determine the signs of DKA requiring insulin administration are the following:

- Glucose greater than or equal to ( $\geq$ ) 250 mg/dL
- Ketone levels above 1.5 mmol/L
- With symptoms of nausea, vomiting and/or abdominal pain
- If ketone levels do not return to less than or equal to ( $\leq$ ) 1.5 mmol/L after 2 hours of oral hydration or IV fluids the subject will be referred to an emergency department and clinic procedures are stopped
- Administer oral hydration with sugar free, caffeine free liquids (if subject is able to drink) or IV fluid hydration (if needed):
  - 22 years and older: 100 cc/hour of 0.9 NS for 2 hours
  - 2-21 years: rate for IV fluid hydration is 10 cc/kg given over 2 hours
  - The maximum saline infusion rate is 30 cc/kg for 2-6 year olds

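### For hyperglycemic-challenge subjects aged 14-21 who develop ketonemia, Protocol Sections 11.1 and 10.5.4 give different IV saline rates

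*Protocol*

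**What the plan says.** **Section 11.1, Potential Risks, row on hyperglycemic challenges.** Among the treatments listed is "IV fluid administration with 0.9 NS will at a rate of 100 cc per hour if ketonemia develops". No age, weight or duration is attached. Among the preventive measures in the same row is "Follow the Ketone management instructions per protocol".

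**Section 10.5.4, ketone treatment guidelines.** The rate is split by age. For ketones from 0.6 to 1.5 mmol/L the two lines are "22 years and older: 100 cc/hour of 0.9 normal saline (NS) for 2 hours" and "2-21 years rate for IV fluid hydration is 10 cc/kg given over 2 hours". The same split recurs for ketones above 1.5 and below 3 mmol/L, for 3 mmol/L and above, and for signs of DKA ("2-21 years: rate for IV fluid hydration is 10 cc/kg given over 2 hours"). Each branch offers oral hydration, with IV fluid as the alternative where needed. The section heading is "Treatment Guidelines Based on Ketones (Investigator Discretion May Be Used for Medical Management".

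**Who is challenged.** In Section 8.1, for ages 14-80, "subjects with a known insulin sensitivity ratio and insulin carbohydrate ratio will be randomly assigned to undergo hypoglycemic and hyperglycemic challenges". In Section 9.1, "subjects (2 - 13 years) will not participate in hypoglycemic and hyperglycemic challenges".

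Detailed challenge management is in separate Hyperglycemic Challenge Guidelines, cited in Sections 8.2.2.6.3 and 10.5.6. They are not among the documents reviewed.

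**The concern.** The Section 11.1 figure equals the rate that Section 10.5.4 reserves for age 22 and older, but it appears without that restriction. The age split in Section 10.5.4 recurs in every branch, so it does not look accidental. For challenge subjects aged 14-21 the two sections therefore state different rates for the same event.

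The protocol itself treats fluid volume as a safety matter. Section 11.1 lists edema and congestive heart failure as risks of saline infusion, and dehydration as a risk of the hyperglycemic challenge. Two sites could each follow a written instruction and give volumes that differ several-fold. Section 11.1 also tells readers how the risk is treated, and for ages 14-21 that description does not match the titled treatment section.

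**Working it through.** No sample-size, power or alpha formula applies. The check is a unit conversion and a comparison of the sections.

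**1. Inputs.**
- Section 11.1: 100 cc/hour, all ages.
- Section 10.5.4, age 22 and older: 100 cc/hour for 2 hours.
- Section 10.5.4, ages 2-21: 10 cc/kg over 2 hours.
- Challenge ages: 14-80 (Sections 8.1 and 9.1).
- Body weight at ages 14-21: not given in the documents. Assumed 40-90 kg.

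**2. The plan's own figure.** For age 22 and older, both sections give 100 cc/hour. Over the 2 hours in Section 10.5.4 this is 100 × 2 = 200 cc. There is no conflict in that age range.

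**3. Age overlap.** Challenges start at 14 and the weight-based rate runs through 21. The conflict is confined to challenge subjects aged 14-21.

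**4. Conversion.** 10 cc/kg over 2 hours is 5 cc/kg/hour, so the hourly rate is 5 × weight in kg. The rates are equal when 5 × weight = 100, that is at 20 kg. The 2-hour totals below apply the Section 11.1 rate for 2 hours, although that section states no duration.

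| Assumed weight | Section 10.5.4, ages 2-21 | Section 11.1 | Ratio | 2-hour totals |
|---|---|---|---|---|
| 40 kg | 200 cc/h | 100 cc/h | 2.0 | 400 vs 200 cc |
| 50 kg | 250 cc/h | 100 cc/h | 2.5 | 500 vs 200 cc |
| 70 kg | 350 cc/h | 100 cc/h | 3.5 | 700 vs 200 cc |
| 90 kg | 450 cc/h | 100 cc/h | 4.5 | 900 vs 200 cc |

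A wider assumed range of 35-100 kg gives 175-500 cc/hour, a ratio of 1.75 to 5. The size depends on the assumed weights. The conflict does not, since it holds at any weight other than 20 kg.

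**5. What depends on the response to hydration.**

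| Branch of Section 10.5.4 | Role of the ketone level after 2 hours of hydration |
|---|---|
| 0.6 to 1.5 mmol/L | No stop based on ketone fall; symptoms trigger the stop |
| Above 1.5, below 3 mmol/L | Stop if ketones have not fallen to 1.5 mmol/L or less |
| 3 mmol/L or above | Procedures already stopped; the result decides emergency referral |
| Signs of DKA | Already a subject stopping rule (Section 10.10.1); the result decides emergency referral |

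Section 10.10.1 also stops a subject whose ketones persist at 1.5 mmol/L or above after hydration. None of these criteria is tied to an infusion rate, and Section 10.5.4 counts oral hydration towards them.

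**6. Precedence.** Nothing in Section 11.1 or 10.5.4 says which rate prevails where they differ.

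**The case against.** The strongest answer is that Section 11.1 is a risk summary and Section 10.5.4 is the operative treatment section. The row sends readers to the ketone instructions, and its 100 cc/hour can be read as an incomplete restatement of the Section 10.5.4 rate for age 22 and older. On that reading an alert site would go to Section 10.5.4 and find the age split. Section 10.5.4 also leaves room for oral fluid and investigator discretion, and the Hyperglycemic Challenge Guidelines may already settle the rate. All of this lowers the severity. It does not remove the contradiction: the pointer is listed under prevention and the fixed rate under treatment, the row leads to a section that disagrees with it for ages 14-21, and neither section gives an order of precedence.

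A reader might infer two stronger claims. The documents support neither.

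- *That at least 24 subjects are affected.* Twenty-four is the enrolment minimum for ages 14-17. To be affected, a subject must have known insulin ratios, undergo a hyperglycemic challenge, develop ketonemia after a start normally conditional on ketones of 0.6 mmol/L or less, and need IV fluid. At least 20 subjects in the 14-80 group are under observation only. The number aged 18-21 is not stated. The affected count could be zero.
- *That stopping decisions depend on which section the site reads.* The 2-hour criteria apply only in some ketone bands, do not mention a rate, and are not in the Section 11.1 row. The documents do not show that the rate difference would change ketone clearance enough to alter a decision.

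**Conclusion.** The inconsistency stands, in a narrow form. The Section 11.1 rate, read as written, does not match Section 10.5.4 for challenge subjects aged 14-21 who develop ketonemia and need IV fluid. The factor of 2.0 to 4.5 rests on the assumed 40-90 kg and is illustrative. That the rates differ at any weight except 20 kg follows from the text alone.

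It is a safety-relevant wording inconsistency of limited severity that should be corrected. It is not a flaw in the design. What the separate challenge guidelines say remains unchecked. No view is taken here on which rate is clinically right.

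**What to change.** Reconcile the hyperglycemic-challenge row of Section 11.1 with Section 10.5.4 so that one passage governs the saline rate for ketonemia and the other refers to it without restating a figure. The sponsor's medical team decides the clinical content. At the same time, check that the Hyperglycemic Challenge Guidelines agree with the result. The cost is about one line in a protocol amendment and a short bulletin to sites. The SAP needs no change.

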# CIP324 Clinical Investigation Plan

10838519DOC

Version H

Page 127 of 173

Medtronic

	

Transfer to ER or follow DKA guidelines of the local institution for the disposition of subject if subject is exhibiting signs and symptoms of DKA

Risks with hypoglycemic challenges	Prevention and Mitigation
Risks for hypoglycemia may include: 

Seizure

Coma

Altered mental status

Loss of consciousness

Cardiovascular event

Death

Risk of rebound hyperglycemia with ketosis

	
Prevention and Mitigation include:
 

Follow frequent blood sampling per protocol (See Section 10.5.1)

Clear guidelines for management during hypoglycemic challenge

IV access to give immediate dextrose or other emergency drugs

Qualified investigator presence during experiment.

Limiting the time the subject is allowed to stay in the hypoglycemic ranges

The subject is under constant observation and monitoring at all times during the challenges

Preventing subjects who do not have a carb/insulin ratio from participating in the challenge (observational only)

Investigational centers are to use glucose meter in the event a YSI blood glucose value is not available at the required time interval.

 
Treatment of these risks include:
 

Rescue therapy treatment instructions are provided in the Hypoglycemic and Hyperglycemic Challenge Guidelines

IV administration of dextrose if uncooperative orally with food or liquid

Glucagon if subject does not respond to Dextrose

Immediate withdrawal from study if severe hypoglycemia (stop the challenge, stop the FST and DO NOT continue with any future scheduled frequent sampling days)

 
Transfer to ER or follow severe hypoglycemia guidelines of the local institution for the disposition of subject.

---

**Medtronic Confidential**

This document is electronically controlled

056-F275, vA Clinical Investigation Plan Template

# CIP324 Clinical Investigation Plan

10838519DOC

Version H

Page 128 of 173

Medtronic

Risks with exercise:	Prevention and Mitigation

Risks for exercise may include:
 

• Hyperglycemia: DKA, symptomatic ketosis, cardiovascular event and dehydration.

• Hypoglycemia: seizure, coma, altered mental status, loss of consciousness, cardiovascular event and death and risk of rebound hyperglycemia with ketosis.

• Musculoskeletal injury: sprain and bone fracture.

• Cardiovascular event

	
Prevention and Mitigation include:
 

• Follow frequent blood sampling per protocol (See Section 10.5.1)

• Clear guidelines for management during both hypoglycemic and hyperglycemic challenge

• IV access to give immediate insulin or dextrose

• Qualified Investigator presence during experiment

• Stopping challenge procedures if ketones are elevated or if subject is exhibiting signs and symptoms of DKA (Please refer to the ketone management guidelines in the protocol)

• Limiting the time the subject is allowed to stay in the hypoglycemic and hyperglycemic ranges

• The subject is under constant observation and monitoring at all times during the challenges

• Preventing subjects who do not have a carb/insulin ratio from participating in the challenge (observational only)

• Investigational centers are to use glucose meter in the event a YSI blood glucose value is not available at the required time interval.

 
Treatment of these risks include:
 

• IV insulin for hyperglycemia if needed

• IV dextrose for severe hypoglycemia

• Rescue therapy treatment instructions are provided in the protocol or hypoglycemia and hyperglycemia

• Immediate withdrawal from study if subject is exhibiting signs and symptoms of DKA or severe hypoglycemia (stop the challenge, stop the FST and DO NOT continue with any future scheduled frequent sampling days)

• If there is a suspected sprain or bone fracture, the subject will be sent to the Urgent care or ER.

• Calling 911 and then transfer to ER

**Medtronic Confidential**

This document is electronically controlled

056-F275, vA Clinical Investigation Plan Template

## **11.2. Potential Benefits**

Subjects are not expected to benefit from participation in this study; however, they may gain increased awareness of emerging technologies for diabetes management as a result of their participation.

## **11.3. Risk-Benefit Rationale**

The benefit of new CGM technology may potentially improve overall diabetes management and glucose control. This benefit outweighs the risks of using the study device and study procedures.

## **11.4. Risk Determination**

In the opinion of the sponsor, this study is considered to be a significant risk (SR) study. Results of an evaluation of the requirements per 21 CFR Part 812.3, led to the SR determination as follows:

Although the devices used in the study do not present any significant risk to subjects, the study will involve hypo and hyperglycemic challenges that presents a potential serious risk to subjects.

Therefore, submission of an Investigational Device Exemption (IDE) application to the United States FDA is required (due to the risk associated with testing performed during the study).

## **11.5. Subject Compensation and Indemnification**

Subjects will be paid for participation. Refer to the ICF on the details of the subject's compensation.

## **12. Adverse Event Assessments**

Throughout the course of the study, investigational centers will make all efforts to remain alert to possible reportable adverse events (AEs) or untoward findings. The study personnel will elicit reports of AEs from the subject at each visit (including phone calls) documenting the medical diagnosis, date of event start and end, causality (relationship to device or procedure), treatment, outcome, and description that includes the details of the event.

